3.8.2 Clinical Data

Datasets: Intent-to-Treat (ITT) and Per-Protocol (PP) analyses were used.

Normally distributed continuous data were described as mean \pm standard deviation, and inter-group comparisons for normally distributed variables used independent-samples t-tests. Non-normally distributed scale data will be described as medians and interquartile ranges, and the Mann–Whitney U non-parametric test will be used for statistical analysis. Categorical data were analyzed using the Chi-square test.

All statistical analyses were performed using SPSS or R software. Statistical significance was set at $P < 0.05$.

四、Ethics and Participant Protection

Before the study begins, the study protocol (including questionnaires and the informed consent form) will be submitted for review and approval to the Ethics Committee of Taizhou People's Hospital Affiliated to Nanjing Medical University (ethics number: LSKY 2025-175-01). Any amendments to the study protocol will be submitted to the Ethics Committee for approval and record-keeping. All participants will be fully informed about the study purpose, procedures, potential risks, and benefits, and will provide written informed consent.

五、References

- [2] de Oliveira Rodrigues DM, Menezes PR, Machado Ribeiro Silotto AE, et al. Efficacy and Safety of Auricular Acupuncture for Depression: A Randomized Clinical Trial [J]. *JAMA Netw Open.* 2023;6(11):e2345138.

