3.7 Observational Indicators

Resting-state functional magnetic resonance imaging was used to conduct pre- and post-intervention comparative analyses in participants receiving auricular acupuncture.

Data collection is divided into two stages:

Baseline: Collection of demographic data, baseline fMRI scan, and clinical assessment (T0).

post-intervention:fMRI scan and clinical assessment immediately after the intervention (T1).

Primary Outcome Measure

Functional connectivity strength between the insula and the medial prefrontal cortex (MPFC)(T1-T0)

This connectivity strength serves as a proxy for the efficiency of information exchange between the “interoceptive hub” and “the self-referential/emotion-regulatory hub”. An increase following auricular acupuncture may reflect enhanced psychosomatic integration and top-down emotional regulation, suggesting a functional optimization of this circuit. Conversely, a decrease could indicate a disruption of pathological hyper-connectivity related to emotional constraint or an upregulation of control—mechanisms consistent with the observed alleviation of emotional symptoms

Secondary Outcome Measures

①Local brain activity indicators:regional homogeneity (ReHo), amplitude of low-frequency fluctuation (ALFF), fractional ALFF (fALFF)(T1-T0);

ReHo captures the temporal synchrony of neural activity within local brain regions. Following auricular acupuncture, increased ReHo in regions such as the insula and prefrontal cortex may reflect improved neural coordination and functional integration. Conversely, decreased ReHo in specific areas could indicate a modulatory effect on abnormally elevated local synchrony.

ALFF reflects the intensity of spontaneous neural activity in the brain. An increase in ALFF within emotion- and cognition-related regions following auricular acupuncture may indicate an elevation in baseline neural activity or metabolic activity in these areas. Conversely, a decrease in ALFF in regions such as the limbic system could reflect an

inhibitory modulatory effect of the intervention on hyperactivity, potentially contributing to emotional stabilization.

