fALFF: Changes in fALFF following the intervention allow a more specific assessment of auricular acupuncture's regulatory effects on intrinsic neural oscillations related to cognition and emotion. When interpreted in conjunction with ALFF changes, the direction of fALFF alteration can help elucidate the specific mechanisms through which auricular acupuncture modulates neural activity patterns.

②Interhemispheric coordination index: voxel-mirrored homotopic connectivity (VMHC)

The VMHC value quantifies the functional coordination between homotopic regions across the two cerebral hemispheres. Following auricular acupuncture, enhanced VMHC in regions associated with emotional regulation and cognitive control, such as the prefrontal cortex and anterior cingulate cortex, may suggest improved interhemispheric balance and integration of emotional processing. Conversely, changes in VMHC within specific regions could help clarify how the intervention modulates functional imbalances between hemispheres, particularly those related to constrained emotional states.

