3.8 Functional Image Processing and Statistical Analysis

3.8.1 Resting-state fMRI Data Processing

All functional imaging data were processed and analyzed using MATLAB R2022b (MathWorks) with the SPM12 toolkit, RESTplus v1.25, and DPABI v7.0 software packages. The preprocessing steps included: ①data format conversion; ②removal of the first 10 time points to eliminate unstable initial signals; ③head motion realignment and slice-timing correction. Individuals with head movements exceeding 2 mm or 2 degrees were removed; ④spatial normalization to the Montreal Neurological Institute template using the DARTEL registration algorithm, followed by resampling to an isotropic voxel size of $3\text{ mm} \times 3\text{ mm} \times 3\text{ mm}$; ⑤spatial smoothing using a 6-mm Gaussian kernel; ⑥linear detrending; ⑦regression of nuisance covariates, including 24-head motion parameters, white-matter signal, and cerebrospinal fluid signal; ⑧application of a 0.01 to 0.08 Hz bandpass filter.

Mean Regional Homogeneity (mReHo): ReHo maps were generated by calculating

Kendall's coefficient of concordance (KCC) using RESTplus V1.25 software. To minimize individual differences, the ReHo value of each voxel was normalized by dividing it by the global mean ReHo value of the entire brain, resulting in mReHo.

Mean Amplitude of Low-Frequency Fluctuation (mALFF) and its derived metric, mean fractional ALFF (mfALFF): The time series of each voxel was transformed into the frequency domain using a Fast Fourier Transform (FFT) to obtain the power spectrum. ALFF was calculated as the square root of the power spectrum. fALFF was defined as the ratio of the ALFF value in the low-frequency range (0.01–0.08 Hz) to the ALFF value across the entire frequency range (0–0.25 Hz). To minimize individual variability, the fALFF value of each voxel was normalized by dividing it by the global mean fALFF value of the whole brain, resulting in the mfALFF.

Functional images were transformed into a mirrored space after preprocessing. The mean BOLD time series for each voxel was extracted. Pearson's correlation coefficients were computed for mirrored voxels from the bilateral hemispheres to produce VMHC maps. The Fisher-z transform was used to enable subsequent group-level comparisons.

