Z-score normalized Functional Connectivity (zFC) values: Brain regions exhibiting significant between-group differences in functional metrics were defined as regions of interest (ROIs). Functional connectivity between each ROI and the entire brain was computed using the RESTplus software. The resulting correlation coefficients were subsequently standardized using Fisher's r-to-z transformation to obtain zFC values.

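### No multiplicity correction or map-level threshold is stated for the group comparison of ReHo, ALFF, fALFF and VMHC maps, although regions called significant become the connectivity seeds

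*Combined protocol and SAP*

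**What the plan says.** Section 3.7 lists four secondary imaging metrics: ReHo, ALFF, fALFF and VMHC. Section 3.8.1 describes preprocessing in detail and explains how each metric is computed, voxel by voxel. On software it says: "All functional imaging data were processed and analyzed using MATLAB R2022b (MathWorks) with the SPM12 toolkit, RESTplus v1.25, and DPABI v7.0 software packages".

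On group inference 3.8.1 says little. For VMHC: "The Fisher-z transform was used to enable subsequent group-level comparisons". For seeds: "Brain regions exhibiting significant between-group differences in functional metrics were defined as regions of interest (ROIs", followed by "Functional connectivity between each ROI and the entire brain was computed using the RESTplus software". It names no test, mask, voxel threshold, cluster rule, family-wise or false-discovery correction, permutation procedure, or adjustment across metrics or seeds.

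The one decision rule comes at the end of 3.8.2 Clinical Data, after the t-test, Mann-Whitney and chi-square tests: "All statistical analyses were performed using SPSS or R software. Statistical significance was set at $P < 0.05".

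The only voxel-level threshold anywhere is in 3.3 Sample Size. There the cited methods study is said to need at least 12 subjects at a threshold of 0.05, which the plan itself calls liberal, at the level of a single voxel.

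The primary outcome in 3.7 is a single quantity: "Functional connectivity strength between the insula and the medial prefrontal cortex (MPFC)(T1-T0".

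**The concern.** In 3.8.1 the word significant decides which regions are reported for the secondary metrics and which become seeds. Without a definition, neither the regions nor the seed maps built on them are pre-specified, and several corrections or cluster rules could be chosen after the maps have been seen.

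The planned interpretation offers no check on this. Section 3.7 gives a meaning to change in either direction and leaves the locations open. For ReHo: "Conversely, decreased ReHo in specific areas could indicate a modulatory effect on abnormally elevated local synchrony". For VMHC: "Conversely, changes in VMHC within specific regions could help clarify how the intervention modulates functional imbalances between hemispheres". A region that arose by chance would fit the planned account as well as a real one, and would then generate connectivity results of its own.

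**Working it through.** **The plan's own figure.** The plan states no error rate for the maps, so there is none to reproduce. The 12-subject figure in 3.3 comes without an effect size or variance, so it cannot be recomputed. It is not disputed here.

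**Which rule applies to the maps?**
- Reading A: the 3.8.2 sentence covers all statistical analyses, so P<0.05 governs the maps, with no correction stated.
- Reading B: the sentence belongs to Clinical Data and to SPSS or R, while imaging is analysed in SPM12, RESTplus and DPABI. The maps then have no rule.

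On neither reading is a correction given.

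**Is the search voxelwise?** This is inferred. Section 3.8.1 computes the metrics at each voxel and picks regions by significance, and 3.7 does not fix the regions. No sentence states the search space.

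**Chance voxels under Reading A.**
- Inputs: voxel size 3 × 3 × 3 mm = 27 mm³ (3.8.1); level 0.05 (3.8.2); mask of 45,000 to 70,000 voxels (assumed; the plan gives none).
- Mask volume: 45,000 × 27 mm³ = 1.2 L; 70,000 × 27 mm³ = 1.9 L.
- Expected false voxels per null map = mask × 0.05: 45,000 × 0.05 = 2,250; 70,000 × 0.05 = 3,500.
- VMHC pairs mirrored voxels, so it has about half as many distinct tests: 1,125 to 1,750.

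**Would these look like regions?** Null two-sample t maps were simulated at 16 versus 16, two-sided uncorrected p<0.05, with 58,719 voxels, assumed map smoothness of 6 to 12 mm FWHM and 30 runs per setting. On average about 2,900 to 3,000 voxels passed per map. They formed on average about 640 clusters at 6 mm, 320 at 8 mm, 180 at 10 mm and 110 at 12 mm. About 20 to 44 clusters per map had 20 or more voxels, and every run had at least one of that size.

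**Across metrics, if each is already held at 5%.**
- Independent: 1 − 0.95⁴ = 0.185.
- Equally correlated (assumed; 60,000 simulated null trials, 16 versus 16): 0.159 at correlation 0.5 and 0.116 at 0.8.
- With 0.05/4 = 0.0125 per metric, independent: 1 − 0.9875⁴ = 0.049.

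These figures cover the four metrics only. Each seed opens a further whole-brain search that they do not count.

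**Price of a stricter threshold.** At 16 versus 16 and two-sided, 80% power at 0.05 needs a standardised difference of about 1.02 (noncentral t, 30 df). The same effect has about 26% power at voxel p<0.001. Cluster-level inference behaves differently, so this is only a guide.

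**The case against.** The strongest reply is that the P<0.05 sentence was never meant for maps: it closes the clinical section and names other software, and the imaging packages can apply corrections. This stands in part. A reader might infer that the trial thresholds its maps at uncorrected 0.05, and the documents do not show that. The threshold in 3.3 does not show it either, since it describes a cited study used for sample size. What the text supports is an unspecified map threshold. That software offers a correction does not mean that one was chosen in advance.

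Second, the voxel counts depend on an assumed mask and on an inferred voxelwise search. That is fair, and they are presented as conditional. The metric-level figure needs neither assumption, but it does depend on how correlated the metrics are.

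Third, one might multiply the regions mentioned in 3.7 by the four metrics and quote a much larger error rate. The documents do not support this: those regions are examples, fALFF has none, and no such list of tests is planned.

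Fourth, 3.8.1 stops at computing zFC values. A group test of those maps is implied by the purpose of the seeds but not stated, and zFC from data-derived seeds is not among the listed secondary outcomes.

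**Conclusion.** The gap is real and should be fixed. Nowhere does the plan state a correction, mask or threshold for the group maps, yet seed selection depends on significance. That omission is certain; its size is conditional. If P<0.05 is applied voxelwise as written, about 2,250 to 3,500 voxels pass by chance in each null whole-brain map, given an assumed mask of 45,000 to 70,000 voxels. If each metric is already controlled at 5%, the chance of at least one false metric is 18.5% under independence, and about 16% or 12% at assumed correlations of 0.5 or 0.8.

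A reader might infer that the primary result is compromised. The documents do not establish that: one insula-MPFC pair fixed in advance needs no whole-brain correction. Nor do they establish that it is safe, because 3.8.1 describes only data-derived seeds and no section defines the insula or MPFC region.

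**What to change.** In 3.8.1:
- State that uncorrected P<0.05 does not apply to maps, and name the software and rule that govern map inference.
- Before group maps are examined, fix the analysis mask and one recognised two-tailed corrected threshold, used for all group maps and for seed selection. One example is voxel p<0.001 with cluster-level family-wise error p<0.05 by permutation; other recognised corrections would serve.
- Say whether zFC maps are compared between groups. Label the four secondary metrics and all seed-based zFC results exploratory, or adjust across metrics and seeds.
- Define the insula and MPFC regions in advance. Keep P<0.05 for that single primary test and for the clinical comparisons in 3.8.2.
- Parts of the text are in the past tense. If group maps have already been examined, say so and report the map results as exploratory.

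In 3.3, add that the cited 0.05 single-voxel basis does not apply to corrected maps.

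Cost: an amendment, which the ethics section says goes to the Ethics Committee, and some computing time. Fewer regions and seeds will survive, and voxel-level power will be lower than a 0.05 threshold implies. No extra participants are needed.
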